## 16. Statistical analysis method

Statistical analysis will be performed using SPSS software. (SPSS version 22.0, IBM Corporation, Armonk, NY, USA),

Continuous variables (variables expressed as mean  $\pm$  standard deviations) will be compared using an independent t-test or Mann-Whitney U test, and categorical variables (including the presence of urinary retention and other adverse events) will be compared using a chi-squared test (or Fisher's exact test). Data are expressed as mean  $\pm$  standard deviation, median (25; 75 median), or number of patients (%). If the p-value is less than 0.05, it is considered to have statistical significance.

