## 4. Research necessity and background

Post-COVID-19 conditions are a novel and poorly understood clinical disease with life-affecting ramifications, and recent studies have shown that patients have worsened their autonomic nervous system after COVID-19 and are potentially at risk of autonomic dysregulation/autonomic neuropathy.

Currently, most patients undergoing general anesthesia are using neuromuscular blockers, and the residual effect of neuromuscular block delays the recovery of autonomic functions of the body after surgery, and causes problems such as deterioration of bladder and bowel function after surgery. Therefore, reverse premise is used for postoperative muscle relaxation recovery, and clinically, sugammadex and neostigmine have been used a lot. Sugammadex generally provides rapid recovery, including recovery from muscle relaxation after surgery, compared to neostigmine, but postoperative outcomes have been reported with limited coverage in postoperative patients. Therefore, in this study, we

expect that sugammadex will help restore bowel function and lung function more than neostigmine after surgery in patients who have recovered from COVID-19 infection.

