#### Exclusion criteria

1. Patients currently infected with COVID-19.
2. 1 Patients under 9 years of age or over 70 years of age
3. Patients who are planning to use a heart-lung machine during surgery (e.g., open-heart surgery, heart transplantation, lung transplantation, etc.)
4. Patients who are expected to undergo surgery within one hour or are scheduled to leave the hospital within 48 hours after surgery
5. Those who show active lesions on lung imaging images during preoperative screening or who are expected to be difficult to remove intubation immediately because endotracheal intubation maintenance is required for postoperative breathing management
6. Those who are hypersensitive to Benzodiazepines, propofol, remifentanyl, fentanyl citrate, rocuronium bromide, sugammadex, flumazenil, and other anesthetics
7. Those with myasthenia gravis or myasthenia gravis syndrome
8. Those with cognitive impairment who cannot understand the instructions and consent manual of this study
9. Other cases where the researcher determines that he or she is not suitable for participating in this study

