#### 7. Postoperative pain control

In the postanesthetic recovery room (PACU), 30 mg ketorolac is administered intravenously as a rescue analgesic as a first-line rescue medication, followed by an additional 50 µg fentanyl (up to 2 doses).

In a general hospital room, tramadol 37.5 mg/acetaminophen 325 mg is administered orally three times from the time of drinking water. If bowel function has not yet recovered or pain cannot be controlled with oral medications, nalbuphine 10 mg, pethidine 25 mg, and tramadol 100 mg are administered intravenously in that order. If the patient has adverse reactions to narcotic analgesics, 100 mg of ketoprofen or 1 g of propacetamol are administered.

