#### 10. End-point timeline

The occurrence of urinary retention after surgery is measured at 1 hour, 24 hours, and 48 hours, respectively, based on the arrival time in the postoperative recovery room.

The first fart time is measured from the time you arrive in the recovery room after surgery.

Two days after surgery, chest X-ray imaging is performed to check for changes in radiological aeration such as pneumonia infiltration, lobe, segmental and segmental atelectasis.

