#### 15. Effectiveness evaluation items and methods

Study endpoints

Primary endpoints

Whether urinary retention occurs 1 hour after surgery

Secondary endpoints

Surgery time and anesthesia time

Recovery time after anesthesia

Intraoperative bleeding, vital signs

Whether and how to administer additional sugammadex

Bladder volume assessed at 1 hour postoperative (summing of autologous urination volumes)

Recovery score and pain score assessed at 1 hour after surgery

First fart time

Whether urinary retention occurs at 24 or 48 hours after surgery

Presence of acute lesions on chest x-ray 2 days after surgery

Actual use of pain and nausea control medications

Other intraoperative events (such as arousal (open eyes), involuntary movements, adverse events and unexpected side effects)

Independent variables

Patient gender, age, weight, height

American Academy of Anesthesiology Physical Classification (ASA class)

Heart rate, blood pressure, oxygen saturation (SpO2), muscle relaxation monitoring score (TOF)

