### **(2) Continuous safety monitoring plan of the target person**

In a clinical trial in patients undergoing general anesthesia and MAC anesthesia, researchers continuously monitor the patient's hemodynamic signs during the general anaesthesia and MAC sedation period. The duration of the double-blind examination is from the selection of the patient group to the primary endpoint 1 hour after surgery to the exit from the recovery room after confirming whether urinary retention occurs, and then up to 48 hours after surgery to check whether specific complications occur and determine whether the complications are relevant to the clinical trial. Details of the award are as follows: (relevant/irrelevant, start, end, last observation: recovered/recovering/not recovering/recovered but with sequelae/death/unknown)

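### Does first flatus time need a stated end of observation and a rule for patients who have not yet passed flatus?

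*Combined protocol and SAP*

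**What the plan says.** Section 15 lists "First fart time" among the secondary endpoints. Section 13, item 10, defines its origin: "The first fart time is measured from the time you arrive in the recovery room after surgery". The same item gives urinary retention three fixed times (1, 24 and 48 hours) and the chest X-ray a fixed day, but gives flatus no last check.

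Section 16 covers the endpoint only through its general rule that continuous variables "will be compared using an independent t-test or Mann-Whitney U test". It names no time-to-event method and no handling of an event not yet observed. Section 17 removes dropouts from the analysis, which does not cover a patient who stays in the study without flatus. Section 21, on statistical planning and interim analysis, is marked as not applicable.

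Three other places bear on the point:

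- Section 4 says that the investigators "expect that sugammadex will help restore bowel function and lung function more than neostigmine".
- Section 8 excludes patients "scheduled to leave the hospital within 48 hours after surgery".
- Section 22(2) follows patients "up to 48 hours after surgery to check whether specific complications occur", which concerns complications and not flatus.

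**The concern.** Time to first flatus is a time-to-event outcome. A t-test or a Mann-Whitney test needs a value or a rank for every patient, and someone with no flatus at the last check has no observed time. If the field is blank, software drops that patient by default. The patients dropped are the slowest to recover. If one drug shortens recovery throughout, more of them come from the slower arm, so a real difference shrinks and power falls.

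Such patients are plausible after abdominal surgery planned to exceed an hour. The ward analgesia rule in Section 13, item 7, has a branch that begins "If bowel function has not yet recovered or pain cannot be controlled with oral medications", although that clause is about the route of analgesia and does not show that anyone lacks flatus when observation ends. Bowel function is one of the two recoveries that Section 4 expects to improve, and flatus is its only measure.

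**Working it through.** **Inputs from the plan.** Section 7 gives 6/38 = 15.8% and 1/39 = 2.6%, two-sided 0.05, power 0.90, 1:1 allocation, dropout of 10% or more, and 112 per group. No figure is given for flatus.

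**The plan's own figure.** The standard two-proportion formula gives 99 per group, and 99/0.9 = 110. Exact Fisher power first reaches 90% at 101 per group (0.902), and 101 × 1.1 = 111.1, which rounds up to 112. The planned size is reproduced, and about 101 per group would be evaluable.

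**Assumptions for flatus.** Log-normal times with log-SD 0.5, 101 per arm, and a common end of observation *c*. The share without flatus at *c*, for median *m*, is 1 − Φ(ln(*c*/*m*)/0.5):

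- *m* = 36, *c* = 48: ln(1.333)/0.5 = 0.575, so 28%.
- *m* = 30, *c* = 48: ln(1.6)/0.5 = 0.940, so 17%.
- *m* = 36, *c* = 96: ln(2.667)/0.5 = 1.962, so 2.5%.
- *m* = 30, *c* = 96: ln(3.2)/0.5 = 2.326, so 1%.

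**Mann-Whitney power (4000 simulated trials per scenario).**

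| Medians (h) | Stop (h) | Without flatus | Ranked last | Left out |
|---|---|---|---|---|
| 36 / 30 | 48 | 28% / 17% | 0.70 | 0.37 |
| 36 / 30 | 72 | 8% / 4% | 0.71 | 0.58 |
| 36 / 30 | 96 | 2.5% / 1% | 0.71 | 0.66 |
| 45 / 36 | 48 | 45% / 28% | 0.83 | 0.35 |
| 45 / 36 | 96 | 6% / 2.5% | 0.87 | 0.79 |
| 24 / 20 | 48 | 8% / 4% | 0.71 | 0.58 |
| 20 / 16 | 48 | 4% / 1.4% | 0.87 | 0.83 |

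With medians 24 and 20 h and a 96 h stop, the loss is under 0.01. With equal medians (30 or 36 h), leaving patients out rejects in 0.047 to 0.054 of trials, so there is no false-positive inflation. At 36/30 h and 48 h, a log-rank test has power 0.65, against 0.70 for Mann-Whitney with patients without flatus tied last and 0.71 with all times known.

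**Dependence on the shape.** Exponential times have a longer tail, and the loss then persists. With a control median of 24 h and a 20% shorter comparator median, the mean difference of 6.9 h falls to 1.2 h at a 48 h stop and is still only 3.6 h at 96 h. With normal times (SD 10 h, control median 36 h) it falls from 7.2 to 5.7 h at 48 h and not at all at 96 h.

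**Direction.** Take log-normal times with log-SD 0.3, medians 24 h (control) and 19.2 h (sugammadex), and a few patients in each arm very late, at 120 h. The means without the late patients are 24 × e^0.045 = 25.1 h and 19.2 × e^0.045 = 20.1 h, a difference of 5.0 h.

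- 10% late in both arms: the true difference is 0.9 × 5.02 = 4.5 h, and omission gives 5.0 h.
- 5% late on control, 10% on sugammadex: the true difference is (0.95 × 25.10 + 0.05 × 120) − (0.90 × 20.08 + 0.10 × 120) = 29.85 − 30.08 = −0.2 h (−0.3 h in simulation), and omission gives 5.0 h.

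The same pattern appears in power. With medians 24/20 h, log-SD 0.5, a 96 h stop and 5% against 10% very late, Mann-Whitney power is 0.34 ranked last and 0.68 left out. Omission therefore understates the difference under a uniform shift and can overstate it otherwise.

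**The sections read together.** The large losses need three things at once: a stop near 48 h, medians of roughly 24 h or more, and omission of patients without flatus. The 48 h times in the plan belong to urinary retention and to complications. Planned stays run beyond 48 h because of the exclusion in Section 8. A clock with a start and no stop reads most naturally as recording until the event, and then no patient lacks a value and the loss is zero.

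**The case for a change.** The strongest case for acting is that the rule is cheap and hard to restore later. One or two sentences and one field (not yet, with the time of the last check) would settle it, and the time of the last check may not be recoverable after discharge. Nothing obliges staff to go on asking after 48 h, when every other timed assessment has ended. Because the bias can go either way, an unstated rule could be chosen after the data are seen, and the 5% rejection rate found for each rule alone does not cover picking between them.

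Much of this stands. The text is silent, the power figures reproduce, and good practice is to report the number without flatus in each arm. But it shows a detail left unstated and not a wrong method. Mann-Whitney is already in the plan and handles patients without flatus properly when they are tied last at a common cut-off, with almost no loss. A switch to log-rank would cost a little power, and if discharge times differ, censoring at discharge assumes that discharge is unrelated to bowel recovery, which is doubtful. No section tells the analyst to drop these patients; that step is supplied by the critic.

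**Conclusion.** The gap is real but does not call for a change. Followed as written, the plan records each patient from recovery-room arrival to first flatus and compares the times with a test that suits skewed data. An analyst who meets a few patients without flatus would rank them last and report how many there were in each arm.

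The possible harm ranges from nothing (all followed to flatus) through about 0.05 of power (36/30 h, 96 h stop) to about half the power (36/30 h, 48 h stop: 0.70 to 0.37). It is larger for long-tailed times and reversed in direction if late recoveries cluster in the otherwise faster arm. All of these figures rest on assumed distributions, assumed stop times and an assumed omission, none of which the documents give. Flatus is one of about eleven secondary items, no power is claimed for it, and the primary endpoint and the 112 per group are unaffected.

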## 7. Number of target subjects and basis for calculation

In this study, based on the results of the previous paper reported by Han et al., the target number of subjects was calculated as follows (Jiwon Han, Ah-Young Oh, Yong-Tae Jeon, Bon-Wook Koo, Bo Young Kim, Donghyun Kim, Insung Hwang. Quality of Recovery after Laparoscopic Cholecystectomy Following Neuromuscular Blockade Reversal with Neostigmine or Sugammadex: A Prospective, Randomized, Controlled Trial. *J. Clin. Med.* 2021, 10, 938. <https://doi.org/10.3390/jcm10050938>).

The primary variable was based on the frequency of dysuria (6/38 vs 1/39) and the number of samples was checked using the G\*Power program. The allocation ratio for both patients was 1, significance 0.05, and power 0.9, set as a two-tailed test and expected the dropout rate to be more than 10%, and calculated the number of test subjects as 112 per group, a total of 224.

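### Sex, age and surgery duration are recorded but never enter the analysis as covariates; the crude tests are valid but give up a little precision, most clearly for 1-hour bladder volume

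*Combined protocol and SAP*

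**What the plan says.** Section 15 gives the primary endpoint as "Whether urinary retention occurs 1 hour after surgery". Among the secondary endpoints are bladder volume at 1 hour and surgery time. Under a separate heading for independent variables it lists "Patient gender, age, weight, height" and "American Academy of Anesthesiology Physical Classification (ASA class", together with vital signs and the TOF score.

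Section 16 is the whole analysis plan. Continuous variables "will be compared using an independent t-test or Mann-Whitney U test, and categorical variables", urinary retention expressly among them, go to chi-squared or Fisher's exact test. It contains no regression, stratified test or adjusted estimate. Section 21, where further statistical planning would stand, is marked as not applicable.

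Section 13 describes 1:1 allocation from a computer-generated list and names no stratification factor. In the same section the reversal agent is given after the TOF check at the end of surgery.

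Section 7 sizes the trial: "The primary variable was based on the frequency of dysuria (6/38 vs 1/39"), with "The allocation ratio for both patients was 1, significance 0.05, and power 0.9, set as a two-tailed test". It "expected the dropout rate to be more than 10" per cent and "calculated the number of test subjects as 112 per group, a total of 224".

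**The concern.** The protocol labels some variables as independent but gives none of them a part in any comparison between arms. Neither the allocation nor the analysis takes account of prognosis. Sex, age and the time the bladder has had to fill are plausible predictors of 1-hour bladder volume, and so of retention. This is a judgement; the documents give no association.

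Two things are at stake. The first is precision: a covariate that explains outcome variation narrows the treatment comparison at no cost in patients. The second is interpretation. If the arms happen to differ in sex or duration, the plan has no adjusted result named in advance, and any adjustment would be chosen after the data had been seen.

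Surgery time is also in an odd place. As a secondary endpoint it would be tested between arms, yet surgery is over before the reversal agent is given, so the drug cannot affect it. It is more useful as a covariate than as an outcome.

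**Working it through.** **Inputs.** From section 7: rates 6/38 = 15.8% and 1/39 = 2.6%, 1:1 allocation, two-sided alpha 0.05, power 0.90, dropout 10%. Assumed: about 100 evaluable patients per arm after dropout, and all covariate strengths.

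**1. The plan's own figure.** The mean rate is (0.1579 + 0.0256)/2 = 0.0918. The effect size is w = [(0.1579 − 0.0256)/2] / √(0.0918 × 0.9082) = 0.229. Total N = (1.960 + 1.282)² / 0.229² = 200.3, rounded up to 201. Then 201/0.90 = 223.3, rounded up to 224, or 112 per group. The stated size is reproduced, and it belongs to the unadjusted chi-squared test. At 100 per arm that test has 90.6% power by formula (Fisher 89.9%); simulation of the uncorrected chi-squared test gives about 94%.

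**2. Events.** 100 × 0.158 + 100 × 0.026 = 15.8 + 2.6, about 18 in total and about 3 in the lower-rate arm. A model with treatment and three covariates has four slopes, so 18.4/4 = 4.6 events per slope. The chance of no events in the lower-rate arm is (38/39)^100 = 7.4%.

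**3. Chance imbalance under simple randomisation.** For sex, assuming half of each: P(difference of at least 10 points) = 2[1 − Φ(0.10/√(0.5/100))] = 16%. For one continuous covariate: P(standardised difference above 0.2) = 2[1 − Φ(0.2/√(2/100))] = 16%. For at least one of four independent covariates: 1 − 0.843⁴ = 50%. The effect is modest: with an assumed sex odds ratio of 2 to 3, a 10-point sex imbalance moves the risk difference by 0.6 to 0.9 points, against a planned difference of 15.8 − 2.6 = 13.2 points.

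**4. Power for retention, crude chi-squared against adjusted logistic likelihood-ratio test.** Simulated at 100 per arm with 3,000 to 4,000 trials per row; simulation error is about 0.4 points per figure.

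| Rates | Assumed covariates | Crude | Adjusted |
|---|---|---|---|
| 15.8% vs 2.6% | four, OR 1.0 per SD | 93.9% | 94.3% |
| 15.8% vs 2.6% | four, OR 1.25 per SD | 93.3% | 93.9% |
| 15.8% vs 2.6% | four, OR 1.5 per SD | 93.3% | 94.5% |
| 15.8% vs 2.6% | four, OR 2.0 per SD | 94.0% | 96.4% |
| 15.8% vs 5% | sex 2, age 1.5 per 10 years, duration 1.5 per hour | 73.9% | 75.7% |
| 15.8% vs 5% | sex 3, age 1.8 per 10 years, duration 1.8 per hour | 75.3% | 80.1% |

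The gain is about 0 to 2.5 points at the planned rates and about 2 to 5 at the smaller effect. Part of it comes from changing the test rather than from adjusting. With odds ratios 2/1.5/1.5 at the planned rates, chi-squared gave 93.9%, a crude likelihood-ratio test 94.1% and the adjusted one 94.7%.

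**5. Type I error of the adjusted likelihood-ratio test.** With both arms at 5%, it was 6.3% against 4.6% for chi-squared in one set of runs. In another, with a Mantel-Haenszel fallback for an arm without events, it was 6.6 to 6.9% against 4.7 to 4.8%. With both arms at 2.6% and no fallback, it was 8.3% against 4.6%.

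**6. Bladder volume.** If covariates explain a share R² of its variance, the standardised effect rises by 1/√(1 − R²). A comparison with 80% crude power has noncentrality 1.960 + 0.842 = 2.802, so adjusted power is Φ(2.802/√(1 − R²) − 1.960). For assumed R² of 0.10, 0.20 and 0.30 this is 84%, 88% and 92%.

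**The case against.** The strongest reply is that nothing is broken. In a randomised trial the crude test already allows for chance imbalance, and 16% for a 10-point sex difference is what randomisation ordinarily produces. The trial is sized for the crude test and reaches its target. Every gain above rests on assumed covariate strengths, and the largest needs strong predictors together with a weaker effect than planned. A heading in translated text does not promise a regression. All of this stands, and it limits the point to precision and pre-specification.

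A reader might go further in four ways that the documents do not support:

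- *That the recorded variables are not used at all.* Surgery time is a listed secondary endpoint, so section 16 would compare it between arms. The general test rules could also serve a baseline table of sex, age and ASA class. The gap is only that none is a covariate.
- *That the primary comparison is biased or underpowered.* Step 1 shows otherwise.
- *That an adjusted logistic test should replace the primary test at no cost.* Step 5 shows a cost when events are sparse. Low rates cannot be excluded, because the planning figures rest on 6 + 1 = 7 events.
- *That surgery duration is a baseline variable in the strict sense.* Section 13 randomises after screening and consent, so duration is measured after randomisation. It is still usable: it is fixed before the reversal agent is given, and the patient and anaesthesiologist are blinded. Anaesthesia time does not share this property if it runs on to extubation, which follows reversal.

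**Conclusion.** The point holds as a modest, inexpensive improvement. Section 16 gives no covariate role to variables that section 15 already collects, and no stratification factor is named. The planned tests remain valid. The loss for the primary endpoint is roughly 0 to 2.5 points of power at 15.8% vs 2.6%, and up to about 5 points at 15.8% vs 5%. The case is clearer for continuous 1-hour bladder volume, where 80% crude power would become 84 to 92% if covariates explained 10 to 30% of the variance.

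These sizes assume 100 evaluable patients per arm, independent covariates, no effect modification and covariate strengths that the documents do not give. The retention gains were computed with a likelihood-ratio test that is itself slightly liberal, so they are better read as upper figures for a method that holds its level.

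**What to change.** Add to section 16, before unblinding, wording to this effect:

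- Bladder volume at 1 hour is analysed by a linear model on treatment, sex, age and surgery duration, reporting the adjusted mean difference with a 95% confidence interval.
- The chi-squared test (or Fisher's exact test) remains the primary test of urinary retention at 1 hour, with the crude risk difference and its confidence interval.
- One supportive adjusted analysis of retention is reported alongside. Name one of two in advance: penalised (Firth) logistic regression on treatment, sex, age and surgery duration, or a Mantel-Haenszel risk difference stratified by sex.
- Surgery duration means time to the end of surgery, recorded before the reversal agent is given. It is described by arm and not tested as an efficacy outcome.

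ASA class, weight and height are left out of the adjusted retention analysis on purpose, because about 18 events will not support more terms.

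The cost is a few sentences and a little analysis work, with no new data and no extra patients. Confirm that the SPSS version named in section 16 offers the chosen method, or name another package. The restriction to accept is that an ordinary likelihood-ratio logistic test should not take over as the primary test.

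### Section 16 lets any secondary comparison with p<0.05 be called significant, with no testing order or exploratory label, and the expected bowel and lung benefits rest only on secondaries

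*Combined protocol and SAP*

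**What the plan says.** Section 16 compares continuous variables by t-test or Mann-Whitney test. For the rest, "categorical variables (including the presence of urinary retention and other adverse events) will be compared using a chi-squared test", with Fisher's exact test as the alternative. It closes with "If the p-value is less than 0.05, it is considered to have statistical significance", a rule that does not distinguish the primary from other endpoints.

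Section 15 lists one primary endpoint at one time point, then eleven secondary lines. Several lines hold more than one comparison, for example "Whether urinary retention occurs at 24 or 48 hours after surgery". Adverse events appear in the last line.

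Section 7 sizes the trial for the primary variable alone: "The allocation ratio for both patients was 1, significance 0.05, and power 0.9, set as a two-tailed test".

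Section 4 gives the scientific expectation. The investigators "expect that sugammadex will help restore bowel function and lung function more than neostigmine after surgery". Section 15 places the matching measures, first flatus and the chest film two days after surgery, among the secondaries.

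No section sets a testing order among secondaries, adjusts for multiplicity or labels any endpoint exploratory. Section 21, whose heading covers the planning of the statistical analysis, is marked as not applicable.

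**The concern.** The plan protects its error rate for one endpoint but allows the word significant for all of them. That matters more here than in many trials, because the hypothesis in the background section is about bowel and lung function while the primary endpoint is urinary. If the primary shows nothing and first flatus or the chest film gives p<0.05 by chance, section 16 permits a significance claim on the very benefit that section 4 expects, and nothing else in the plan restrains it. Section 16 also plans no confidence intervals, so the p-value would not be accompanied by a statement of how large or small the effect could be.

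**Working it through.** **1. The plan's own figure.** Inputs from section 7: 6/38 = 15.8% and 1/39 = 2.6%, two-sided 0.05, power 0.90, 1:1 allocation, dropout taken as 10%.

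- Mean proportion 0.0918, difference 0.1323.
- n = [1.96 × √(2 × 0.0918 × 0.9082) + 1.2816 × √(0.158 × 0.842 + 0.0256 × 0.9744)]² / 0.1323² = 98.05, so 99 per group.
- 99 / 0.9 = 110 per group, against the stated 112. An exact Fisher calculation (power 89.9% at 100 and 90.5% at 102 per group) points to about 101, and 101 × 1.1 = 111.1, which rounds up to 112.

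The stated size is reproduced within two patients per group. It spends the full 0.05 on the primary, so that endpoint's type I error stays at 5%.

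**2. Counting secondary comparisons.** Splitting the eleven lines of section 15 in order, with vital signs and intraoperative events counted once each: 2+1+2+1+1+2+1+2+1+2+1 = 16.

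- Reversal is given at the end of surgery (section 13). Removing surgery time, bleeding, vital signs and intraoperative events leaves 12: anaesthesia time, recovery time, additional sugammadex, bladder volume, recovery score, pain score, first flatus, retention at 24 h, retention at 48 h, chest film, analgesic use and antiemetic use.
- Anaesthesia time is mostly surgery time. Recovery time and additional sugammadex are poor candidates for no difference, because section 4 already takes faster recovery with sugammadex as background. Removing these three leaves 9.

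**3. Chance of at least one p<0.05 with no true difference.** For k independent tests:

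- Either direction: 1 − 0.95^k. k = 12 gives 0.460; k = 9 gives 0.370.
- Favouring sugammadex: 1 − 0.975^k. k = 12 gives 0.262; k = 9 gives 0.204.

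The documents give no correlations. For equal pairwise correlation ρ, with normal test statistics sharing a common factor g and c = 1.96, the either-direction chance is 1 − ∫ φ(g) [Φ((c − √ρ g)/√(1−ρ)) − Φ((−c − √ρ g)/√(1−ρ))]^k dg. The one-direction chance drops the second Φ term.

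| Comparisons | Direction | ρ = 0 | ρ = 0.3 | ρ = 0.5 |
|---|---|---|---|---|
| 12 | either | 46% | 40% | 32% |
| 12 | favours sugammadex | 26% | 20% | 16% |
| 9 | either | 37% | 33% | 27% |
| 9 | favours sugammadex | 20% | 17% | 13% |

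A single test has 5% and 2.5%. For the two endpoints behind section 4 alone, taken as independent, the figures are 1 − 0.95² = 9.8% and 1 − 0.975² = 4.9%.

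**4. Which test decides the primary.** Section 16 allows chi-squared or Fisher without saying which governs. They can disagree: an illustrative 7/101 against 1/101 gives uncorrected chi-squared p = 0.030 and Fisher p = 0.065, with a Newcombe 95% interval for the difference of 0.3% to 12.7%. A rule that turns on the primary being significant therefore needs one named test.

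**The case against.** Several points on the other side stand.

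- **The plan does have a hierarchy at the top.** Section 15 separates one primary from the secondaries and section 7 sizes the trial on it. A reader might infer that nothing at all is ordered; the gap lies only among and around the secondaries.
- **A false recovery benefit is not likely.** A reader might infer this from the either-direction figures. Those include results favouring neostigmine, and even 46% is below one half. Counting all 16 comparisons as independent gives 1 − 0.95^16 = 56%, but that set includes surgery time, bleeding, vital signs and intraoperative events. In the sugammadex direction the range is 13% to 26%.
- **The figures lean high.** Retention at 24 and 48 hours is one outcome repeated, and bladder volume at 1 hour is the continuous form of the primary. Fisher's test is conservative for uncommon events: with 101 per arm and a common 5% rate, its true size is about 2%.
- **No section says that a significant secondary would count as trial success.** Section 4 states an expectation, not a decision rule. How a chance result would be reported is a prediction.
- **Adverse events.** A reader might infer that testing them at 0.05 conceals harm. Missing rare harms is a matter of low power, not multiplicity, and section 18 already plans frequencies, rates, listings, severity and causality.

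What these points leave untouched is that section 16, followed as written, permits a significance claim on any secondary whatever the primary shows.

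**Conclusion.** The concern holds in a limited form. The primary is sound on this point. The secondaries have no order, no adjustment and no exploratory label, and the endpoints that carry the expected bowel and lung benefits are among them. With 9 to 12 comparisons and correlation from 0 to 0.5, the chance of at least one false p<0.05 is about 27% to 46% in either direction and 13% to 26% in favour of sugammadex. The count of tests, the equal correlations and the absence of any true difference are assumptions, and conservative exact tests would lower the figures. The documents support neither a probable false benefit nor any inflation of the primary's error rate. This is a cheap improvement to the wording, not a flaw in the design.

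**What to change.** Replace the last sentence of section 16 with:

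> Statistical significance (two-sided 0.05) is claimed only for the primary endpoint, using one named test fixed before unblinding, and reported with a risk difference and 95% CI. All secondary endpoints are reported as between-group differences with 95% CIs and described as exploratory. Adverse events are tabulated as in section 18, with risk differences and 95% CIs.

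Optionally, if the sponsor wants confirmatory claims on bowel and lung function, pre-specify a fixed sequence after the primary, gated on that same named test. Which endpoints enter and in what order is the sponsor's choice.

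The cost is a few sentences. Secondary results with p<0.05 could no longer be called significant, and under the optional sequence a failed primary would bar any confirmatory claim on bowel or lung. The primary keeps its full 0.05, so its power and the sample size are unchanged.
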